1.1. Study Objectives

The primary objectives of this study are as follows:

- To evaluate the steady-state pharmacokinetics (PK) and confirm age-appropriate dose of SOF/VEL/VOX FDC in pediatric subjects with chronic HCV infection

The secondary objectives of this study are as follows:

- To evaluate the safety and tolerability of SOF/VEL/VOX FDC in pediatric subjects with chronic HCV infection
- To evaluate the antiviral efficacy of SOF/VEL/VOX FDC treatment in pediatric subjects with chronic HCV infection, as assessed by the proportion of pediatric subjects with sustained virological response (SVR) 12 weeks after cessation of treatment (SVR12)
- To evaluate the antiviral efficacy SOF/VEL/VOX FDC treatment in pediatric subjects with chronic HCV infection, as assessed by the proportion of pediatric subjects with SVR 4 and 24 weeks after cessation of treatment (SVR4 and SVR24)
- To evaluate the proportion of pediatric subjects with virologic failure, including on-treatment virologic failure and relapse
- To evaluate the kinetics of circulating HCV RNA during treatment and after cessation of treatment
- To evaluate the emergence of viral resistance to SOF, VEL, and VOX during treatment and after cessation of treatment
- To evaluate the effect of SOF/VEL/VOX FDC on growth and development of pediatric subjects during and after treatment
- To evaluate acceptability, including palatability, and swallowability of formulations (as applicable) used in the study
- To assess the effect of treatment with SOF/VEL/VOX FDC on quality of life as measured by PedsQL™ Pediatric Quality of Life survey including neuropsychiatric assessments

CCI

1.2. Study Design

This is an open-label, multi-cohort study evaluating the PK, safety, and antiviral activity of SOF/VEL/VOX FDC in pediatric subjects with chronic HCV infection.

Overall, the study will enroll both direct-acting antiviral (DAA)-naïve and DAA-experienced pediatric subjects with chronic HCV infection of any HCV genotype. Three sequential age-based cohorts will be enrolled:

- Cohort 1: at least 20 subjects 12 to < 18 years old
- Cohort 2: at least 20 subjects 6 to < 12 years old
- Cohort 3: at least 20 subjects 3 to < 6 years old

Eligible DAA-naïve subjects without cirrhosis will receive treatment for 8 weeks. Eligible DAA-naïve subjects with cirrhosis and DAA-experienced subjects with or without cirrhosis will receive treatment for 12 weeks.

The total time to complete all study visits is up to approximately 36 weeks for subjects treated with 8 weeks of therapy and 40 weeks for subjects treated for 12 weeks of therapy including the following periods:

- 28-day (4-week) screening period
- 8 or 12-week treatment period
- 24-week posttreatment period

The schedules of assessments for the study are provided as appendices to the SAP (see Study Procedures Table, [Appendix 1](#)).

1.3. Sample Size and Power

Assuming similar variability for SOF, GS-331007, VEL, or VOX AUC_{tau} in the pediatric population compared to adults, a sample size of 20 pediatric subjects per cohort will provide at least 80% power to target a 90% confidence interval of the geometric mean ratio (GMR) within the bounds of 50% to 200% when comparing with the adult population.

2. TYPE OF PLANNED ANALYSIS

2.1. DMC Analyses

An external multidisciplinary Data Monitoring Committee (DMC) will review the progress of the study and perform interim reviews of the safety data in order to protect subject welfare and preserve study integrity. To ensure the best interests of the participants, the DMC will recommend to the sponsor if the nature, frequency, and severity of adverse effects associated with the study treatment warrant the early termination of the study, the continuation of the study, or the continuation of the study with modifications.

The DMC's role and responsibilities and the scope of analysis to be provided to the DMC are provided in a mutually agreed upon charter, which defines the DMC membership, meeting logistics, and meeting frequency.

2.2. Final Analysis

The European Medicines Agency (EMA) granted Gilead a waiver to study SOF/VEL/VOX in children under 12 years of age. As a result, after all adolescent subjects (12 to < 18 years of age) have completed through the post-treatment week 24 visit or have prematurely discontinued from the study, outstanding data queries have been resolved, and the database has been cleaned and finalized, the final analysis of the data will be performed.

3. GENERAL CONSIDERATIONS FOR DATA ANALYSES

Analysis results will be presented using descriptive statistics. For categorical variables, the number and percentage of subjects in each category will be presented; for continuous variables, the number of subjects [n], mean, standard deviation [SD] or standard error [SE], median, first quartile [Q1], third quartile [Q3], minimum, and maximum will be presented.

Data collected in the study will be presented in by-subject listings for all subjects in the Safety Analysis Set, unless otherwise specified. All by-subject listings will be presented by subject identification (ID) number in ascending order, unless otherwise specified.

3.1. Analysis Sets

Analysis sets define the subjects to be included in an analysis. Analysis sets and their definitions are provided in this section. The number of subjects eligible for each analysis set will be provided. Subjects who were excluded from Safety and Full Analysis Sets will be provided in a by-subject listing with reasons for exclusion.

3.1.1. All Enrolled Analysis Set

All Enrolled Analysis Set includes all adolescent subjects enrolled in the study after screening.

3.1.2. Full Analysis Set

The Full Analysis Set (FAS) includes HCV infected adolescent subjects who were enrolled into the study and received at least one dose of study drug. The study drug in this study is SOF/VEL/VOX FDC.

This is the primary analysis set for efficacy analyses.

3.1.3. Safety Analysis Set

The Safety Analysis Set includes all adolescent subjects who took at least 1 dose of study drug (ie, SOF/VEL/VOX FDC).

This is the primary analysis set for safety analyses.

CCI

[REDACTED]

[REDACTED]

[REDACTED]

Population PK Analysis Set

The Population PK Analysis Set includes all enrolled adolescent subjects who received at least one dose of study drug and for whom at least one non-missing PK concentration data value is available from all types of PK sampling. This is the primary analysis set for the Population PK modeling and PK exposure analyses.

The PK Analysis Set is equivalent to the Population PK Analysis Set.

3.2. Subject Grouping

For analyses based on the All Enrolled Analysis Set or FAS, subjects will be grouped according to the treatment to which they were enrolled. For analyses based on the Safety Analysis Set, subjects will be grouped according to the actual treatment received. The actual treatment received is defined as the enrolled treatment except for subjects who received treatment that differs from the enrolled treatment for the entire treatment duration. In this case, the actual treatment received is defined as the treatment received for the entire treatment duration. Given the fact that only DAA-naïve subjects without cirrhosis have been enrolled in this study, there will be only one treatment group (ie, SOF/VEL/VOX FDC 8 weeks).

The efficacy analyses will be performed on the FAS, and for selected efficacy analyses, by HCV genotype (1 [further broken down to 1a and 1b], 2, 3, 4, 5, 6, or other, as appropriate, and total). The safety analysis will be performed on the Safety Analysis Set.

For other selected analyses, for example, the summary of responses to the acceptability and palatability questionnaire, the analysis of tanner pubertal stage assessment data, please refer to the relevant sections for the detailed description of subject grouping.

3.3. Strata and Covariates

This study does not use a stratified randomization schedule for enrolling subjects. No covariates will be included in efficacy and safety analyses.

3.4. Examination of Subject Subsets

The efficacy endpoint SVR12 will be analyzed for the following subsets:

- sex (male, female)
- race (black, non-black)
- ethnicity (Hispanic or Latino, non-Hispanic or Latino)
- baseline weight (\leq median, $>$ median)
- IL28B (CC, non-CC [further broken down to CT, TT])

- baseline HCV RNA ($< 800,000$ IU/mL, $\geq 800,000$ IU/mL)
- baseline alanine aminotransferase (ALT) ($\leq 1.5 \times$ ULN, $> 1.5 \times$ ULN)
- prior HCV treatment experience (treatment naïve, treatment experienced - DAA-naïve, DAA experienced)
- number of prior HCV treatments
- most recent response to prior DAA-naïve and DAA HCV treatment (non-response, relapse/breakthrough) for treatment experienced subjects
- study treatment status (completed study treatment, discontinued study treatment)
- adherence to study drug ($< 80\%$, $\geq 80\%$)

3.5. Missing Data and Outliers

3.5.1. Missing Data

In general, missing data will not be imputed unless methods for handling missing data are specified.

For missing last dosing date of study drug, imputation rules are described in Section 3.7.1. The handling of missing or incomplete dates for adverse event (AE) onset is described in Section 7.1.5.2, and for prior and concomitant medications in Section 7.8.

For analyses of categorical HCV RNA data, missing posttreatment HCV RNA data will have the missing data imputed. Missing on-treatment HCV RNA will have the missing data imputed up to the time of the last dose (for on-treatment displays). If the study day associated with the last dosing date is greater than or equal to the lower bound of a visit window, and the value at the visit is missing, the value will be imputed. If the study day associated with the last dosing date is less than the lower bound of a visit window, then the on-treatment value at that visit will remain missing.

If a data point is missing and is preceded and followed in time by values that are “< lower limit of quantitation (LLOQ) target not detected (TND)”, then the missing data point will be set to “< LLOQ TND”. If a data point is missing and preceded and followed by values that are “< LLOQ detected”, or preceded by “< LLOQ detected” and followed by “< LLOQ TND”, or preceded by “< LLOQ TND” and followed by “< LLOQ detected”, then the missing value will be set to “< LLOQ detected”. In these situations, the data point will be termed a bracketed success; otherwise, the data point will be termed a bracketed failure (ie, \geq LLOQ detected). If a data point is missing and is not bracketed, the missing data point will also be termed a failure (ie, \geq LLOQ detected) except for SVR24, which will be imputed according to SVR12 status. Success for SVR12 who have no further HCV RNA measurements collected will be counted as a success for SVR24 due to the high correlation between these 2 endpoints.

For the analyses of continuous HCV RNA efficacy data, when and only when a missing HCV RNA value is imputed as < LLOQ TND or < LLOQ detected according to the imputation rule described above, the corresponding continuous value will be imputed to LLOQ - 1 IU/mL. No other imputation will be performed for continuous HCV RNA data.

In the analysis of the PedsQL™ Pediatric Quality of Life Inventory V4.0 Short Form (SF15) questionnaire, missing data at on-treatment visits and posttreatment follow-up Week 12 (FU-12) visit will not be imputed. Last posttreatment observation carried forward will be used for imputation of missing data at posttreatment follow-up Week 24 visit.

3.5.2. Outliers

Outliers will be identified during the data management and data analysis process, but no sensitivity analyses will be conducted. All data will be included in the data analysis..

3.6. Data Handling Conventions and Transformations

By-subject listings will be presented for all subjects in the Safety Analysis Set and sorted by subject ID number, visit date, and time (if applicable) unless otherwise specified. Data collected on log forms, such as AEs, will be presented in chronological order within subject.

Age (in years) on the date of the first dose of study drug and sex at birth will be used for analyses and presentation in listings.

If a subject was not dosed with study drug at all, then the date the informed consent was signed will be used instead of the first dose date of study drug. Unless age is captured on the eCRF, the following conventions will be used for the imputation of date of birth when it is partially missing or not collected:

- If only month and year of birth is collected, then “15” will be imputed as the day of birth
- If only year of birth is collected, then “01 July” will be imputed as the day and month of birth
- If year of birth is missing, then date of birth will not be imputed

Non-PK data that are continuous in nature but are less than the LLOQ or above the upper LOQ will be imputed as follows:

- A value that is one unit less than the limit of quantitation will be used for calculation of descriptive statistics if the datum is reported in the form of “< x” (where x is considered the limit of quantitation). For example, if the values are reported as < 50 and < 5.0, values of 49 and 4.9, respectively, will be used for calculation of summary statistics. An exception for this rule is any value reported < 1. For the values reported as < 1 or < 0.1, value of 0.9 or 0.09 will be used for calculation of summary statistics.

- A value that is one unit above the limit of quantitation will be used for calculation of descriptive statistics if the datum is reported in the form of “> x” (where x is considered the limit of quantitation). Values with decimal points will follow the same logic as above.
- The limit of quantitation will be used for calculation of descriptive statistics if the datum is reported in the form of “≤ x” or “≥ x” (where x is considered the limit of quantitation).

The COBAS® AmpliPrep/COBAS® TaqMan® HCV Test, v2.0 for use with the High Pure System was used to determine HCV RNA results in this study. The LLOQ of the assay is 15 IU/mL.

When the calculated HCV RNA value is within the linear range of the assay, then the result will be reported as the “<< numeric value>> IU/mL”. This result will be referred to in this document as the numeric result or as “≥ LLOQ detected” for categorical result.

When HCV RNA is not detected, the result is reported as “No HCV RNA detected” or “target not detected”. This result will be referred to in this document as “< LLOQ target not detected” or “< LLOQ TND”.

When the HCV RNA IU/mL is less than LLOQ of the assay, the result is reported as “< 15 IU/mL HCV RNA detected”. This result will be referred to in this document as “< LLOQ detected”.

The overall category of HCV RNA < LLOQ includes “< LLOQ TND” and “< LLOQ detected.”

For numerical HCV RNA data, values below LLOQ will be set to the LLOQ - 1 IU/mL (ie, 14 HCV RNA IU/mL). HCV RNA values returned as “No HCV RNA detected” will also be set to 14 IU/mL.

If methods based on the assumption that the data are normally distributed are not adequate, analyses may be performed on transformed data (eg, log₁₀ scale) or nonparametric analysis methods may be used, as appropriate.

Natural logarithm transformation will be used for plasma/blood concentrations and analysis of PK parameters. Plasma concentration values that are below the lower limit of quantitation (BLQ) will be presented as “BLQ” in the concentration data listing. Values that are BLQ will be treated as 0 at predose time points, and one-half the value of the LLOQ at postdose time points for summary purposes.

For the presentation of summary and order statistics, if at least 1 subject has a concentration value of BLQ for the time point, then the minimum value will be displayed as “BLQ” If more than 25% of the subjects have a concentration data value of BLQ for a given time point, then the minimum and Q1 values will be displayed as “BLQ” If more than 50% of the subjects have a concentration data value of BLQ for a given time point, then the minimum, Q1, and median values will be displayed as “BLQ” If more than 75% of the subjects have a concentration data value of BLQ for a given time point, then the minimum, Q1, median, and Q3 values will be displayed as “BLQ” If all subjects have concentration data values of BLQ for a given time point, then all order statistics (minimum, Q1, median, Q3, and maximum) will be displayed as “BLQ”.

3.7. Visit Windows

3.7.1. Definition of Study Day

Study day is the day relative to the date of the first dose of study drug. Study Day 1 will be defined as the day of first dose of study drug administration.

Study day will be calculated from the date of first dose of study drug administration and derived as follows:

- For postdose study days: Assessment Date - First Dose Date + 1
- For days prior to the first dose: Assessment Date - First Dose Date

The last dose date for the study drug will be the end date on study drug administration eCRF for the record where the “subject permanently discontinued” flag is ‘Yes’.

If there are subjects for whom the date of last study drug is unknown due to the reason that the subject was lost to follow-up and not able to be contacted, the date of last dose will be estimated using the maximum of nonmissing study drug start or stop dates, visit dates and laboratory collection dates (posttreatment visits and unscheduled visits are not included).

3.7.2. Analysis Windows

Subject visits might not occur on protocol-specified days. Therefore, for the purpose of analysis, observations will be assigned to analysis windows.

In general, the baseline value will be the last nonmissing value on or prior to the first dose date of study drug.

HCV RNA, vital signs, and safety laboratory data collected up to the last dose date + 3 days are considered to be on-treatment data and HCV RNA, vital signs and safety laboratory data collected after the last dose date + 3 days are considered posttreatment data. Given the fact that only DAA-naïve subjects without cirrhosis have been enrolled in this study, the analysis windows for on-treatment HCV RNA, vital signs and safety laboratory data are provided in [Table 3-1](#).

Table 3-1. Analysis Windows for On-treatment HCV RNA, Vital Signs and Safety Laboratory Data

Nominal Visit	SOF/VEL/VOX 8 Weeks		
	Nominal Day	Lower Limit	Upper Limit
Baseline	1	(none)	1
Week 1	7	2	11
Week 2	14	12	21
Week 4	28	22	42
Week 8	56	43	≥ 57

HCV RNA, vital sign, and safety laboratory data collected after the last dose date + 3 days will be assigned to the posttreatment follow-up (FU) visits. Visit windows will be calculated from the last dose date (ie, FU Day = collection date minus the last dose date) as shown in [Table 3-2](#).

Table 3-2. Analysis Windows for Posttreatment HCV RNA, Body Weight, Height, Vital Sign and Safety Laboratory Data

Nominal FU ^a Visit	HCV RNA, Body weight and Height			Vital Signs and Safety Laboratory Data ^b		
	Nominal FU Day	Lower Limit	Upper Limit	Nominal FU Day	Lower Limit	Upper Limit
FU 4	28	21	69	28	4	30
FU 12	84	70	146	NA	NA	NA
FU 24	168	147	210	NA	NA	NA

a FU x visit = posttreatment Week x follow up visit.

b Vital signs (blood pressure, pulse, respiratory rate, and temperature) and safety labs will only be summarized for the FU 4 visit (up to 30 days after last dose).

3.7.3. Selection of Data in the Event of Multiple Records in an Analysis Window

Depending on the statistical analysis method, single values may be required for each analysis window. For example, change from baseline by visit usually requires a single value, whereas a time-to-event analysis would not require 1 value per analysis window.

If multiple valid nonmissing numeric observations exist in an analysis window, records will be chosen based on the following rules if a single value is needed:

- For baseline, the last available record on or prior to the date of the first dose of study drug will be selected. If there are multiple records with the same time or no time recorded on the same day, average (arithmetic mean) will be used for the baseline value.

- For postbaseline visits:

The record closest to the nominal day for that visit will be selected except for HCV RNA posttreatment follow-up visits, for which the latest record in the analysis window will be selected.

If there are 2 records that are equidistant from the nominal day, the later record will be selected.

If there is more than 1 record on the selected day, the average will be taken, unless otherwise specified.

If multiple valid nonmissing categorical observations exist in a window, records will be selected as follows:

- For baseline, the last available record on or prior to the date of the first dose of study drug will be selected. If there are multiple records with the same time or no time recorded on the same day, the value with the lowest severity will be selected (eg, normal will be selected over abnormal).
- For postbaseline visits, follow the same rules described above for postbaseline numeric observations, except that if there are multiple records on the same day, the most conservative value will be selected (eg, abnormal will be selected over normal).

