Appendix 2. Study Procedures Table

Appendix Table 1. Screening and On-Treatment Study Visits

	Screening	Day 1 ^a	On-Treatment Study Week (±3 Days)				End of Treatment ^c	Early Termination ^a
			Week 1	Week 2 ^{4,v}	Week 4 ^f	Week 8 ^b		
Clinical Assessments								
Informed Consent/Assent	X							
Determine Eligibility	X	X						
Medical History	X							
Parental Height, if known		X						
Complete Physical Examination	X	X					X	X
Symptom-Directed Physical Examination			X	X	X	X		
Tanner Pubertal Stage Assessment		X					X	X
Vital Signs ^d	X	X	X	X	X	X	X	X
Body Weight and Height	X	X	X	X	X	X	X	X
Radiographic Bone Age Assessment		X					X	X
AEs and Concomitant Medications	X ^e	X	X	X	X	X	X	X
FibroScan [®] (if available)	X ^f	X ^f						
Pregnancy Prevention Counseling ^g		X			X	X	X	X
SOF/VEL/VOX Swallowability Assessment	X ^h	X ^h						
SOF/VEL/VOX Acceptability Questionnaire ⁱ		X					X	X
Quality of Life Survey ^j		X					X	X

	Screening	Day 1 ^a	On-Treatment Study Week (±3 Days)					Early Termination ^a
			Week 1	Week 2 ^{l,v}	Week 4 ^f	Week 8 ^b	End of Treatment ^c	
Review of Study Medication Compliance				CCI	X	X	X	X
Study Drug Dispensing		X			X	X		
Return of Study Drug Bottles					X	X	X	X
Review Dosing Diary				X ^l	X ^l			
Laboratory Assessments								
Hematology, Chemistry	X	X	X	X	X	X	X	X
Coagulation	X	X					X	X
HCV RNA	X	X	X	X	X	X	X	X
HBV DNA ¹		X	X	X	X	X	X	X
CCI								
Serum or Urine Pregnancy Testing ⁿ	X	X		X ^l	X	X	X	X
Single sparse PK sample collected at anytime			X			X	X	X
Two sparse PK Samples collected pre-dose and between 15 minutes and up to 4 hours postdose				X ^p	X ^p			
CCI								
CCI								
Urinalysis	X	X		X ^l	X ^l			
Urine Drug Screen	X							
IL28B Genotyping	X ^f	X ^f						
Bone Age Biomarkers		X						X ^w

	Screening	Day 1 ^a	On-Treatment Study Week (±3 Days)					End of Treatment ^c	Early Termination ^a
			Week 1	Week 2 ^{t,v}	Week 4 ^f	Week 8 ^b			
HCV Genotyping	X								
HIV testing, HAV Antibody, HCV Antibody, HBsAg, HBsAb, HBcAb	X								
HbA1c Fibrotest [®] , APRI	X								
TSH	X						X	X	
Alpha-1 anti-trypsin	X								
Approximate amount of blood drawn (mL) _ Cohort 1	22.1	12.3	9.3	11.3 ^g CCI CCI	11.3	9.3	13.2	16.8	
Approximate amount of blood drawn (mL) _ Cohort 2	22.1 ^u	12.3	9.3	18 ^t	11.3	9.3	13.2	16.8	
Approximate amount of blood drawn (mL) _ Cohort 3	22.1 ^u	12.3	8.3	8 ^v	9.3	8.3	12.2	12.2	

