4.2.1. Durations of Exposure to Study Regimen

Total duration of exposure to study drug will be defined as last dose date minus first dose date plus 1, regardless of any temporary interruptions in study drug administration, and will be expressed in weeks using up to 1 decimal place (eg, 4.5 weeks).

The total durations of exposure to study drug will be summarized using descriptive statistics (n, mean, SD, median, Q1, Q3, minimum, and maximum) and using the number (ie, cumulative counts) and percentage of subjects exposed through the following time periods: Baseline (Day 1), Week 1 (Day 7), Week 4 (Day 28), and Week 8 (Day 56) given the fact that only DAA-naïve subjects without cirrhosis have been enrolled in this study. A 3-day window is applied to the last planned on-treatment visit to match with the protocol-specified visit window. Summaries will be provided for the Safety Analysis Set.

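### SAP Table 3-1 files Day 11 under Week 1, although on its own nominal days Day 11 is an on-schedule Week 2 day and nearer to Day 14

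*SAP*

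**What the plan says.** SAP 3.7.1 counts the first dose as Day 1: "For postdose study days: Assessment Date - First Dose Date + 1". SAP 3.7.2 assigns observations to windows by study day. Table 3-1, which sets the "analysis windows for on-treatment HCV RNA, vital signs and safety laboratory data", has an 8-week column only: Week 1 is nominal Day 7 with limits 2–11, Week 2 is Day 14 with 12–21, Week 4 is Day 28 with 22–42, and Week 8 is Day 56 from Day 43 on.

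The protocol's schedule (Appendix Table 1) heads these visits "On-Treatment Study Week (±3 Days" and gives no study day for any of them. The same week-to-day equation recurs in SAP 4.2.1, where exposure is counted through "Week 1 (Day 7), Week 4 (Day 28), and Week 8 (Day 56". That section also applies a 3-day window to the last planned on-treatment visit, to match the protocol's visit window.

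For several on-treatment records in one window, SAP 3.7.3 states: "The record closest to the nominal day for that visit will be selected". For ties: "If there are 2 records that are equidistant from the nominal day, the later record will be selected".

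Under SAP 3.5.1, an empty on-treatment HCV RNA visit is imputed when the study day of "the last dosing date is greater than or equal to the lower bound of a visit window, and the value at the visit is missing". It becomes < LLOQ only if the values before and after it are both < LLOQ; "otherwise, the data point will be termed a bracketed failure", that is, ≥ LLOQ. A missing value that is not bracketed is also a failure. SAP 6.2.2 applies these windows and this imputation to the secondary endpoint of HCV RNA < LLOQ by visit.

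**The concern.** Analysis windows exist to absorb visits that miss their planned day. Here, if the printed nominal days are the planned days, a Week 2 visit that is on time but at the early edge of its range is treated as a second Week 1 visit and then discarded. The by-visit response table could therefore show an imputed failure for a subject whose own sample showed response. The Week 2 laboratory and vital-sign summaries would also lose a value that was collected on schedule. A subject who first falls below LLOQ between Weeks 1 and 2 is the natural example.

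**Working it through.** **Inputs.** Nominal days and limits come from SAP Table 3-1, the ±3 days from Protocol Appendix Table 1, the selection and tie rules from SAP 3.7.3, the imputation from SAP 3.5.1, and the planned cohort size (at least 20) from SAP 1.2.

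**Step 1: reproduce the printed upper limits (11, 21, 42).** The SAP states no rule for setting limits, so three were tried.

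| Rule | Midpoints | Upper limits |
|---|---|---|
| Nearest nominal day (7/14/28/56), ties to the earlier visit | 10.5, 21, 42 | 10, 21, 42 |
| Same midpoints, rounded half up | 10.5, 21, 42 | 11, 21, 42 |
| Nearest day on 8/15/29/57, ties to the later visit | 11.5, 22, 43 | 11, 21, 42 |

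The nearest-day rule on the printed days gives the second and third limits but not the first. The 11/12 split appears only if 10.5 is rounded up, or if other anchor days are used.

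**Step 2: where Day 11 belongs on the printed days.** 11 − 7 = 4 and 14 − 11 = 3, so Day 11 is nearer to Week 2. The permitted ranges are 7 ± 3 = Days 4–10 and 14 ± 3 = Days 11–17. Day 11 is inside the second and outside the first.

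**Step 3: selection.** Any Week 1 visit on Days 4–10 is at most 3 days from Day 7. The Day 11 record is 4 days away and always loses. Only a first visit on Day 3 (tie, later record kept) or Day 2, or no other Week 1 record, lets Day 11 be selected, and then it is reported as Week 1. In every case Week 2 is empty unless there is another sample on Days 12–21.

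**Step 4: imputation of the empty Week 2** (last dose on Day 12 or later, Week 1 visit on Days 4–10, Day 11 observed < LLOQ). SAP 3.5.1 does not say whether the preceding value is the one selected for the earlier window or any earlier record, so both readings are shown.

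| Week 1 value | Next value after Week 2 | Selected window values | Any record in time | Limits 2–10 / 11–21 |
|---|---|---|---|---|
| ≥ LLOQ | < LLOQ | imputed ≥ LLOQ | imputed < LLOQ | observed < LLOQ |
| < LLOQ | < LLOQ | imputed < LLOQ | imputed < LLOQ | observed < LLOQ |
| either | ≥ LLOQ or absent | imputed ≥ LLOQ | imputed ≥ LLOQ | observed < LLOQ |

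**Step 5: size.** Day 11 is 1 of the 7 permitted Week 2 days. At n = 20 one false failure is 1/20 = 5 percentage points. As an illustration, assume 15/20 true responders at Week 2: 75.0% (95% Clopper-Pearson CI 50.9–91.3) becomes 14/20, 70.0% (45.7–88.1).

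**Step 6: the opposite convention.** If Weeks 1 and 2 were scheduled on Days 8 and 15, the permitted ranges are Days 5–11 and 12–18, and the 11/12 split fits them exactly. Moving the limit to 10/11 would then push a Day 11 Week 1 visit into the Week 2 window. There a Day 15 record (1 day from Day 14) beats it, and Week 1 is left empty.

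**The case against.** The strongest reply is that nothing in the SAP has been broken. It gives no midpoint or nearest-day rule for window limits; the closeness rule in 3.7.3 chooses among records inside a window. Ordinary half-up rounding yields all three printed limits. The protocol names no study day for Week 2, and if sites counted 14 days after Day 1, the split is right. This stands in part. A reader might infer a plain arithmetic error in the table, and the documents do not support that. They do support an inconsistency: Table 3-1 prints Days 7 and 14, SAP 4.2.1 uses the same convention for Weeks 1, 4 and 8, and on those days the limit excludes an on-schedule visit. If Days 8 and 15 were meant, the nominal-day column that drives selection is the part that is off.

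Second, SAP 3.5.1 speaks of values before and after in time, so the Day 11 result could itself bracket Week 2. This also stands. With Week 1 ≥ LLOQ and Week 4 < LLOQ, the false failure arises only if bracketing uses selected window values. With a later value that is ≥ LLOQ or absent, it arises on either reading.

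Third, the effects are descriptive. Treatment-emergent laboratory abnormalities (SAP 7.2.2.1) count any postbaseline time point up to 30 days after the last dose, and the by-subject listings keep the Day 11 results. That is correct and limits the point.

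**Conclusion.** The point holds as a small internal inconsistency at one boundary. It rests on the printed Days 7 and 14 being the planned visit days. On that basis a Day 11 Week 2 visit drops out of the Week 2 summaries of HCV RNA, laboratory values and vital signs, unless another sample falls on Days 12–21. Categorical HCV RNA can then be reported as ≥ LLOQ despite an observed < LLOQ, under the conditions in the table above. Continuous HCV RNA is either missing at Week 2 or, if bracketed by values < LLOQ, set to LLOQ − 1.

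Three stronger inferences should be resisted. Not every Day 11 response becomes a failure: if Weeks 1 and 4 are both < LLOQ, the category is unharmed. One permitted day in seven is not a frequency, because the documents give no distribution of visit days. The sustained-response results are not in doubt: SVR4, SVR12 and SVR24 use Table 3-2, and the primary PK endpoint does not use these windows.

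**What to change.** Confirm how visit days were counted, then put the nominal days and limits of Table 3-1 on that one convention.

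- If Days 7/14/28/56 are right, set Week 1 to Days 2–10 and Week 2 to Days 11–21. Each ±3-day visit range then lies in its own window, and the 21/22 and 42/43 limits stay as they are.
- If visits were scheduled on Days 8/15/29/57, keep the 11/12 limit and correct the nominal-day column, since record selection uses it.

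A short clause in SAP 3.5.1 saying whether bracketing uses selected window values or any record would settle the imputation as well.

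The edit is a few table cells, by SAP revision or documented in the study report as SAP section 1 allows. The downside is real if the limit is moved without confirming the convention. A Day 11 Week 1 visit could be misfiled, and because entry requires HCV RNA of at least 1000 IU/mL at Screening, the preceding baseline value would normally make the empty Week 1 an imputed failure.
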